9.3.2.2 Outcomes

Death will be defined if there is evidence of a date of death in the database. Cause of death will include respiratory/cardiorespiratory, liver disease, trauma, suicide, transplant-related, other, and unknown.

Organ transplantations will be defined if there is evidence of an organ transplantation. Type of transplant will include lung, liver, kidney, and other.

Hospitalisations will be defined if there is evidence of a start date for a hospitalisation. Reason for hospitalisation includes pulmonary exacerbation, pulmonary complication, GI complication, transplant-related, sinus infection, non-transplant surgery, other.

CF complications include the following:

- CFRD status (impaired glucose tolerance, CFRD with or without fasting hyperglycaemia, CFRD complications [retinopathy, microalbuminuria, chronic renal insufficiency, chronic renal failure requiring dialysis, peripheral neuropathy])
- Hepatobiliary (gall stones, gall stones requiring surgery, liver disease [cirrhosis], cirrhosis complications [oesophageal varices, gastric varices, GI bleed, splenomegaly, hypersplenism, ascites], liver disease [noncirrhosis], hepatic steatosis, liver disease [other])
- Bone/Joints (arthritis/arthropathy, bone fracture, osteopenia, osteoporosis)
- Pulmonary (ABPA, asthma, haemoptysis-massive, pneumothorax requiring chest tube)
- Gastrointestinal (DIOS, fibrosing colonopathy/colonic stricture, GERD, GI bleed [non-variceal] requiring hospitalisation, pancreatitis, peptic ulcer disease, rectal prolapse)
- Other (absence of vas deferens, anxiety disorder, cancer confirmed by histology, depression, hearing loss, hypertension, kidney stones, nasal polyps requiring surgery, renal failure requiring dialysis [cause other than CFRD], sinus disease [symptomatic], other [specify including cataract])

Pulmonary exacerbations will be defined by evidence of a CF care episode with reason pulmonary exacerbation. Respiratory microbiology will include patients with a bacterial culture and evidence of *Staphylococcus aureus*, *Haemophilus influenzae*, *Pseudomonas aeruginosa*, *Burkholderia*, fungal/yeast, other.

Serious safety outcomes will be defined by combining death, organ transplantations, hospitalisations, and selected CF complications.

Pregnancy will be defined if there is evidence of pregnancy in the database. Outcomes include live birth, stillbirth, spontaneous abortion, therapeutic abortion, undelivered, and unknown. Note that the CF Foundation Patient Registry does not have a variable of "congenital abnormality" for pregnancy outcome; however, as part of routine pharmacovigilance activities, Vertex collects unsolicited reports of pregnancy using the Pregnancy Safety Information Collection Form (see [Stand-alone Document 4](#) listed in Annex 1. List of Stand-alone Documents). Matching of pregnancy cases between the unsolicited reports and the CF Foundation Patient Registry data will be as thorough as

possible, with considerations for the anonymous nature of the registry data and for patients from the spontaneous reports who may not be in the registry and vice versa.

Cardiac disease will be defined by specification of cardiac disease as a reason for hospitalisation or as a CF complication.

CF lung disease severity will be defined if there is evidence of pulmonary function test results in the database. Absolute measures (in litres) for FEV₁, best FEV₁ during last period, FVC, and FEF_{25%-75%} are collected. Percent predicted values will be calculated based on the equations of Hankinson et al.³⁰ or Wang et al.³¹ (see Section 9.3.4.4). Pulmonary function data are collected at each encounter. On average, there are 5 pulmonary function measures in a calendar year for each patient. In the US, the standard of care for CF includes quarterly office visits to the CF care centre. Best FEV₁ is identified per calendar quarter for each patient.

Clinical signs of CF disease progression will be defined by outcomes previously specified, including death, organ transplantation, and selected CF complications (e.g., CFRD and DIOS).

Change in lung function over time will be defined by pulmonary function test results over the years in the analysis. Absolute measures (in litres) for FEV₁ (current FEV₁ at each encounter) are collected. Percent predicted FEV₁ will be calculated based on the equations of Hankinson et al.³⁰ or Wang et al.³¹ (see Section 9.3.4.4).

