Hospitalisation	start date of hospitalisation for pulmonary exacerbation	start date (any hospitalisation); reason (pulmonary exacerbation, pulmonary complication, GI complication, transplant-related, sinus infection, non-transplant surgery, other)
CF complications	see Section 9.3.1.2	see Section 9.3.2.2
Pulmonary exacerbations and respiratory microbiology ^a	yes/no; respiratory microbiology	yes/no; respiratory microbiology

Table 4 Comparison of Variables Collected by the Patient Registries

Variables	CF Trust (UK)	CF Foundation (US)
Pregnancy	pregnancy occurrence/outcome/undelivered/unknown; gestational age; presence of congenital anomalies at birth; only for female patients 13 years of age and older	pregnancy occurrence/outcome/undelivered/unknown; only for female patients
Serious safety outcomes	combination of death, organ transplantations, hospitalisations, and selected CF complications	combination of death, organ transplantations, hospitalisations, and selected CF complications
Pulmonary function tests ^b	FEV ₁ (L), best FEV ₁ (L), FVC (L), FEF _{25%-75%} (L) during last period, unable to perform test, not done	FEV ₁ (L), FVC (L), FEF _{25%-75%} (L), unable to perform test
Cardiac disease	as reported in CF complication	as reported in reason for hospitalisation or CF complications
Hepatic impairment	reported as liver disease with portal hypertension	reported as liver disease with complications

CF: cystic fibrosis; FEF_{25%-75%}: forced midexpiratory flow; FEV₁: forced expiratory volume in 1 second; FVC: forced vital capacity; GI: gastrointestinal; UK: United Kingdom; US: United States.

^a Whilst the specific respiratory microbiology variables collected by the CF Trust and the CF Foundation differ, efforts will be made to create general categories for the analyses. Details will be provided in the statistical analysis plan.

^b Percent predicted FEV₁ will be calculated based on the equations of Hankinson et al.³⁰ or Wang et al.³¹ The Hankinson standard will be used for male patients 18 years and older and female patients 16 years and older. The Wang standard will be used for male patients aged 6 to 17 years and for female patients aged 6 to 15 years.

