9.3.4 Statistical Analyses

Data analyses will be performed by the CF Trust and CF Foundation to meet the study objectives. The results of the annual analyses will be reported in the study report.

The primary objectives of this study are to evaluate long-term safety, pregnancy outcomes, drug utilisation, and CF disease progression in patients treated with ivacaftor. Descriptive statistics will be calculated for all endpoints. All safety, pregnancy, and CF disease progression endpoints will be compared between the Ivacaftor and Comparator Cohorts or between the Ivacaftor Pregnancy and Comparator Pregnancy Cohorts. Safety and pregnancy outcomes will also be described for the Historical Cohort. Annual incidence rates will be calculated for safety outcomes (Objective 1). Crude relative risks or risk difference with 95% confidence intervals will be calculated for some outcomes, as appropriate. Statistical modelling with adjustment for confounders and effect modifiers will be conducted, as possible, due to the likely sparse data. Identification of confounders and effect modifiers will be performed using stratified analyses. Each annual report will include the patient data from the previous calendar year (e.g., annual cross-sectional analysis). Longitudinal analyses will be included, as appropriate, in the final report.

This section presents a summary of the planned statistical analyses for this study (see [Stand-alone Document 4](#) listed in Annex 1. List of Stand-alone Documents). A detailed

analysis plan will be presented in a statistical analysis plan. A summary of the comparisons to be made for each objective is provided in Table 5.

Table 5 Comparisons by Primary Objective

Objective	Setting	Cohorts Included	Comparisons
1. To evaluate the long-term safety of ivacaftor in patients with CF	UK, US	Ivacaftor; Comparator; Historical	
 Comparison of long-term safety between the Ivacaftor Cohort (ivacaftor-treated patients) and the Comparator Cohort (concurrent nonexposed patients) to include relative risks or risk differences Descriptive statistics for the Historical Cohort (historical nonexposed patients) will be available for comparison to the Ivacaftor Cohort (ivacaftor-treated patients). Comparisons to be based on 95% confidence intervals.

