9.3.4.2 Pregnancy (Objective 2)

Frequency and outcomes of pregnancies will be analysed for patients exposed to ivacaftor in the Ivacaftor Pregnancy Cohort and for patients in the Comparator Pregnancy Cohort. Pregnancy outcomes include live birth, stillbirth, spontaneous abortion, therapeutic abortion, undelivered, and unknown. Pregnancy outcomes of gestational age and congenital anomalies of the infant will be described for the CF Trust Patient Registry data. Pregnancies will be described by outcome, age, and duration of ivacaftor exposure. Pregnancy outcomes will also be described for the Historical Cohort.

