9.6 Data Management

Data management is maintained at each registry according to their internal processes. Only final analysis tables (i.e., no patient-level data) will be provided to the marketing authorisation holder.

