11 MANAGEMENT AND REPORTING OF ADVERSE EVENTS/ADVERSE REACTIONS

Adverse reactions will not be reported on an expedited basis for this study because it is an observational cohort study designed to collect long-term safety information using secondary data. Safety listings will be received by Vertex annually from the patient registries. Individual case safety reports will be created as applicable to prevent duplicate reports in the global safety database. This is in line with EU Good Pharmacovigilance Practices VI.C.1.2.1, which specifies that, for noninterventional study designs that are based on secondary use of

data, adverse reactions reporting is not required. Reports of adverse events/reactions should only be summarised in the study report, where applicable.

All safety information will be assessed and submitted in analysis reports, which will be submitted according to the schedule agreed as part of the post-authorisation commitment for this study. A full review of the safety information collected for the full study period will be presented in the final study report.

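### Congenital anomalies and gestational age are listed for comparison in the UK and the US, but the US registry collects neither, and the one US source named for anomalies appears to cover exposed women only

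*Protocol*

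**What the plan says.** **Endpoints and comparison.** Section 9.3.3 lists six pregnancy endpoints, among them gestational age and congenital anomalies, without limiting any to one registry. Section 9.3.4 then states: "All safety, pregnancy, and CF disease progression endpoints will be compared between the Ivacaftor and Comparator Cohorts", and continues with the two pregnancy cohorts. Table 5 gives the setting for Objective 2 as UK and US. It also makes the Historical Cohort available for comparison on the basis of 95% confidence intervals.

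**What the US registry holds.** Table 4 gives the US pregnancy variables as "pregnancy occurrence/outcome/undelivered/unknown; only for female patients". The UK entry adds gestational age and anomalies at birth. Section 9.3.2.2 confirms the anomaly gap: "Note that the CF Foundation Patient Registry does not have a variable of" congenital abnormality.

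**What is offered for the US.** The same sentence of 9.3.2.2 goes on to say that "Vertex collects unsolicited reports of pregnancy using the Pregnancy Safety Information Collection Form" as part of routine pharmacovigilance. It then adds: "Matching of pregnancy cases between the unsolicited reports and the CF Foundation Patient Registry data will be as thorough as" possible, given that registry data are anonymous and the two sources overlap only in part.

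**The section specific to Objective 2.** Section 9.3.4.2 says: "Pregnancy outcomes of gestational age and congenital anomalies of the infant will be described for the CF Trust Patient Registry data". It names no US anomaly analysis.

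**Data access.** Section 9.6: "Only final analysis tables (i.e., no patient-level data) will be provided to the marketing authorisation holder". Section 11: "Safety listings will be received by Vertex annually from the patient registries", with individual case safety reports created where applicable to avoid duplicates.

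**The concern.** Pregnancy outcome is one of four primary objectives, and section 7.2 records treatment of pregnant women among the important potential risks in the Risk Management Plan. On two of its endpoints the general analysis rule promises a US comparison for which there are no US registry data, while the specific rule confines them to the UK.

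The mention of unsolicited reports makes this more than a loose cross-reference. It follows directly on the admission that the anomaly field is missing, so it is natural to read it as the way to obtain that information. If anomalies found that way reached the US cohort tables, they could arise only among exposed women. A single matched case might then be read as a signal against a comparator in whom nobody had looked. The limitations in 9.9 cover missing data, selection, differential follow-up and the Historical Cohort, but not a US anomaly source available for one cohort only.

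Separately, the sections on what the sponsor receives do not agree, and 9.3.2.2 does not say who does the case matching or on which fields.

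**Working it through.** The protocol states no rate, sample size or power for congenital anomalies, and Table 6 concerns death only. There is no figure to reproduce, so the check is a comparison of sections.

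**Step 1. Promised against collected.**

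| | UK | US |
|---|---|---|
| Endpoint in 9.3.3 | both, no registry limit | both, no registry limit |
| Cohort comparison, 9.3.4 and Table 5 | yes | yes |
| Gestational age collected (Table 4) | yes | no |
| Anomalies collected (Table 4, 9.3.2.2) | yes | no |
| Described under 9.3.4.2 | yes | not named |

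The US column cannot be satisfied: rows 1 and 2 require what rows 3 to 5 do not supply. This affects 2 of the 6 pregnancy endpoints. On the counts in 9.5, the registry without the variables is the larger one: 1035 / (1035 + 432) = 1035 / 1467 = 71% of the *G551D* patients in the two registries. Those are 2010 counts for all ages and both sexes, so they show only that the gap is in the main data source. They do not give a number of pregnancies.

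**Step 2. Whom the substitute source can reach.** Section 9.1.2.5 requires the Comparator Pregnancy Study Cohort to have no evidence of current or past ivacaftor exposure. Section 9.2.3 describes the Historical Cohort in the same terms. The unsolicited reports come from the sponsor's routine pharmacovigilance. The protocol does not say in so many words that they concern only women on ivacaftor; that is an inference, but a firm one. On it, neither unexposed cohort has any US anomaly source. For US gestational age no substitute is named at all.

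**Step 3. What would follow if the source were used in a contrast.** Let *p*E and *p*C be the true anomaly risks in exposed and comparator pregnancies, and *s*E and *s*C the probabilities that an anomaly is captured. If uncaptured were treated as absent, the expected recorded difference would be

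*s*E × *p*E − *s*C × *p*C.

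With *s*C = 0 this is *s*E × *p*E. It cannot be negative, and it does not depend on *p*C. With equal true risks it still exceeds zero whenever *s*E and the risk do. If uncollected is instead kept as missing, there is no US contrast to compute. Neither outcome is a valid comparison.

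**Step 4. Data access.** Section 9.6 limits the sponsor to final tables. Sections 10.1 and 10.2 deny it subject information and patient records, and 10.3 has analyses presented to it from deidentified data. Section 11 nevertheless sends it annual safety listings to support individual case reports. A listing from which case reports can be made is not a final summary table, so 9.6 and section 11 conflict as worded. Matching under 9.3.2.2 also needs case-level information from both sources. If the sponsor does it, 9.6 stands in the way. If the registry does it, 9.6 is not breached, and 10.3 shows that the CF Foundation receives identifiers.

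**The case against.** The strongest reply is that the protocol plans no US anomaly comparison. Section 9.3.2.2 says that reports exist and will be matched; it does not say that matched anomalies enter the cohort tables. Section 9.3.4.2, the section specific to this objective, describes these outcomes for UK data, and 9.3 warns that the variables need not be identical across registries. The specific rule can be read as narrowing the general one, since 9.3.4 calls itself a summary. This part stands: a biased US contrast is a risk left open, not a declared analysis. It does not remove the conflict, because 9.3.3, 9.3.4 and Table 5 carry no UK limit.

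A reader might go further and infer that the US comparator count will be zero and the relative risk therefore unbounded. The documents do not support this. The zero arises only if an uncollected field is coded as absent, which nothing prescribes. Table 5 also names relative risks or risk differences under Objective 1 only.

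A reader might also infer that the matching is impossible. That does not follow either. The protocol does not assign the task, registry staff could do it, and section 11 gives the sponsor listings. Section 9.3.2.2 openly admits anonymity and partial overlap, although that is a different limitation from one-sided ascertainment.

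Finally, section 11 states that adverse reaction reporting is not required for a secondary-data study, so the access conflict is mainly a matter of consistent wording and not the failure of an endpoint.

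**Conclusion.** The point holds as a conflict between stated rules within a primary objective, and it should be corrected. Sections 9.3.3, 9.3.4 and Table 5 promise a two-country comparison of two endpoints that the US registry does not collect and that 9.3.4.2 describes for the UK only. The only US anomaly source named is, by inference, exposed-only, so using it in any cohort contrast would mean differential ascertainment. Section 9.6 conflicts with section 11 and, conditionally on the sponsor doing the matching, with 9.3.2.2.

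In size, 2 of 6 pregnancy endpoints in one of the two registries are affected. No number of spurious events can be given, because the documents state neither a background anomaly risk nor an expected number of US pregnancies.

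The conclusion rests on one assumption, that unsolicited pharmacovigilance reports concern women who took ivacaftor. The conflict over endpoints does not depend on it.

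**What to change.** 1. In 9.3.3, 9.3.4 and Table 5, restrict the comparative congenital-anomaly and gestational-age endpoints to the UK registry, in line with 9.3.4.2.
2. In 9.3.2.2, state that anomalies from US unsolicited reports are presented only as a separate descriptive series of exposed pregnancies, with the number of reported pregnancies as denominator. State that they are not merged into, or compared with, the US Comparator Pregnancy Study Cohort or the Historical Cohort.
3. In 9.3.2.2, say who does the matching, on which fields and for what purpose.
4. In 9.6, name the de-identified annual safety listing of section 11 as an explicit exception to the rule on patient-level data.

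The cost is protocol wording, plus whatever effort the matching takes once it is assigned. The protocol does not say whether the unsolicited reports carry fields that can be linked to the registry, so that should be settled before the task is given to either party. The protocol would no longer claim a US comparison on these two endpoints, but no valid comparison is lost, since the US data could not support one.

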9.3.2.3 Analysis Variables

Age will be defined using date of birth.

Sex will be defined as reported in database.

Genotype will be defined for each allele and will be categorised by *CFTR* mutation class.^{14,22}

Baseline percent predicted FEV₁ will be defined by most recent value obtained before initiating ivacaftor in the Ivacaftor Cohort; percent predicted FEV₁ will be matched to the most recent available value by calendar date for the Comparator Cohort. Standardised equations (those of Hankinson et al.³⁰ or Wang et al.³¹ [see Section 9.3.4.4]) will be used to calculate percent predicted FEV₁ and will be specified in the statistical analysis plan (see [Stand-alone Document 4](#) listed in Annex 1. List of Stand-alone Documents). Analysis of FVC and FEF_{25%-75%} will also be specified in the statistical analysis plan.

Cardiac disease will be defined by evidence of cardiac disease in reason for hospitalisation or in specified CF complications.

Hepatic impairment will be defined by liver disease with complications (e.g., cirrhosis complications: oesophageal varices, gastric varices, GI bleed, splenomegaly, hypersplenism, ascites).

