8.2 Secondary Objectives

8.2.1 Secondary Objectives for Primary Objective 1

1. To evaluate the long-term safety of ivacaftor amongst patients in the following subgroups:
 - Patients between 6 and 11 years of age
 - Patients with FEV₁ <40% predicted value
 - Patients with cardiac disease
 - Patients with moderate or severe hepatic impairment
2. To evaluate pulmonary exacerbations and bacterial sputum colonisation with long-term ivacaftor treatment

8.2.2 Secondary Objective for Primary Objective 2

To measure the frequency of pregnancy in ivacaftor-treated patients

8.2.3 Secondary Objectives for Primary Objective 3

Off-label use amongst patients within the following subgroups:

- Children less than 6 years of age
- Patients with Class III, non-*G551D-CFTR* mutations
- Patients with non-Class III mutations

8.2.4 Secondary Objectives for Primary Objective 4

To evaluate the effect of ivacaftor on CF disease progression, as measured by

- CF lung disease severity, based on pulmonary function (e.g., percent predicted FEV₁)
- Clinical signs of CF disease progression (e.g., death, transplantation, CFRD, distal intestinal obstruction syndrome [DIOS])
- Change in lung function over time

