9.3.4.1 Safety (Objective 1)

Safety outcomes for the Ivacaftor Cohort and the Comparator Cohort will include 6 main categories: death, organ transplantation, hospitalisations, CF complications, and pulmonary exacerbations and respiratory microbiology, and serious safety outcomes (composite outcome). The safety outcomes will be analysed for the Historical Cohort.

1. Death: Frequency of death will be calculated and will include cause of death and age at death. Analyses will be stratified by duration of ivacaftor exposure, age, sex, *CFTR* genotype class, percent predicted FEV₁, and comorbid conditions.
2. Organ transplantations: Frequency of organ transplantations will be calculated and will include type of organ transplanted and age at transplant. Analyses will be stratified by duration of ivacaftor exposure, age, sex, *CFTR* genotype class, percent predicted FEV₁, and comorbid conditions.

3. Hospitalisations: Frequency of hospitalisations will be calculated and will include the number of days of hospitalisation, and age at hospitalisation. Analyses will be stratified by duration of ivacaftor exposure, age, sex, *CFTR* genotype class, percent predicted FEV₁, and comorbid conditions.
4. CF complications: Frequency of CF complications will be calculated. CF complications include infections, arthritis, asthma, bone fracture, diabetes, and several hepatic, gastrointestinal, and pulmonary complications. Analyses will be stratified by duration of ivacaftor exposure, age, sex, *CFTR* genotype class, percent predicted FEV₁, and comorbid conditions.
5. Pulmonary exacerbations and respiratory microbiology: Frequencies of pulmonary exacerbations and respiratory microorganisms will be calculated. Analyses will be stratified by duration of ivacaftor exposure, age, sex, *CFTR* genotype class, percent predicted FEV₁, and comorbid conditions.
6. Serious safety outcomes: Frequency of serious safety outcomes will be calculated. Analyses will be stratified by duration of ivacaftor exposure, age, sex, *CFTR* genotype class, percent predicted FEV₁, and comorbid conditions.

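### The US cardiac-disease subgroup can be entered through an undated hospitalisation, itself a safety endpoint, so its yes/no hospitalisation and serious-outcome comparisons are conditioned on the outcome

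*Protocol*

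**What the plan says.** Protocol section 8.2.1 names "Patients with cardiac disease" as a subgroup in which long-term safety is to be evaluated. Section 7.2 counts cardiac disease and hepatic impairment among the potential risks taken from the Risk Management Plan, and section 9.3.4.1 stratifies every safety outcome by comorbid conditions.

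The US definition appears three times. Section 9.3.2.3 has "Cardiac disease will be defined by evidence of cardiac disease in reason for hospitalisation or in specified CF complications". Section 9.3.2.2, under outcomes, has "Cardiac disease will be defined by specification of cardiac disease as a reason for hospitalisation or as a CF complication". Table 4 gives the same two routes. None of the three carries a date rule. The UK definition in section 9.3.1.3 uses the complication route only.

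The US endpoint in section 9.3.2.2 reads "Hospitalisations will be defined if there is evidence of a start date for a hospitalisation", and the composite reads "Serious safety outcomes will be defined by combining death, organ transplantations, hospitalisations, and selected CF complications". Section 9.3.3 lists both as safety endpoints, and section 9.3.4 describes each annual report as a cross-sectional analysis of the previous calendar year.

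The reasons that the US registry codes are given as follows: "Reason for hospitalisation includes pulmonary exacerbation, pulmonary complication, GI complication, transplant-related, sinus infection, non-transplant surgery, other".

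**The concern.** A subgroup meant to identify patients at higher risk should be fixed before the events being compared. Here one of its two routes of entry is such an event. Someone admitted for a cardiac reason during the analysis year becomes a subgroup member because of the admission, and the same admission then counts as the hospitalisation endpoint and as a serious safety outcome. This happens in either cohort.

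The missing date rule adds a second problem. The same undated variable serves as both outcome and subgroup marker, so a first cardiac event on ivacaftor places the patient among those who supposedly had cardiac disease already. Membership may then depend on treatment.

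At stake is the US answer to a named secondary objective on a risk that the sponsor itself identified. US hepatic impairment has the same timing gap: "Hepatic impairment will be defined by liver disease with complications", built from cirrhosis complications that section 9.3.2.2 also lists as safety outcomes.

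**Working it through.** **Passages side by side**

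1. Entry: a cardiac hospitalisation reason or a CF complication, undated (9.3.2.2, 9.3.2.3, Table 4).
2. Endpoint: any hospitalisation with a start date, also part of the composite (9.3.2.2, 9.3.3).
3. Window: one calendar year (9.3.4).
4. From 1 to 3, entry by an analysis-year cardiac admission implies both yes/no endpoints with probability 1.
5. Contrast within 9.3.2.3: baseline percent predicted FEV₁ is tied to the last value before ivacaftor, with a calendar-date rule for comparators. Cardiac disease has neither.
6. The seven US hospitalisation reasons include no cardiac one. The US complication list has hypertension but no cardiac disease. Cardiac disease can therefore appear only under the catch-all categories.

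**Illustration of direction**

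The protocol states no figure to reproduce on this point. All inputs below are assumptions:

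- r = 0.30, the comparator risk of any hospitalisation among patients entering by the complication route
- s, the share of the comparator subgroup entering by an analysis-year admission, from 0 to 1
- RR, the true relative risk in the complication route, from 0.6 to 2.0
- k, the rate of entry by admission on ivacaftor relative to comparator, 1 or 2

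Comparator risk: R0 = (1 − s)·r + s.
Ivacaftor risk: R1 = [(1 − s)·r·RR + k·s] / [(1 − s) + k·s].
Observed relative risk = R1/R0.

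Example, s = 0.5, RR = 2.0, k = 1: R0 = 0.5 × 0.30 + 0.5 = 0.65; R1 = 0.5 × 0.60 + 0.5 = 0.80; ratio 1.23.

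Example, s = 0.5, RR = 0.6, k = 2: R1 = (0.5 × 0.18 + 1.0)/1.5 = 0.727; ratio 0.727/0.65 = 1.12.

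| s | R0 | RR 2.0, k = 1 | RR 0.6, k = 1 | RR 1.0, k = 2 | RR 0.6, k = 2 |
|---|---|---|---|---|---|
| 0 | 0.300 | 2.00 | 0.60 | 1.00 | 0.60 |
| 0.25 | 0.475 | 1.47 | 0.81 | 1.22 | 1.07 |
| 0.50 | 0.650 | 1.23 | 0.91 | 1.18 | 1.12 |
| 0.75 | 0.825 | 1.09 | 0.96 | 1.09 | 1.07 |
| 1 | 1.000 | 1.00 | 1.00 | 1.00 | 1.00 |

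With equal entry (k = 1) the ratio moves towards 1 from either side. With unequal entry (k = 2) a null effect looks harmful and a protective one crosses 1. If few enter by admission the distortion is small: at s = 0.05, RR = 2.0, k = 1, the ratio is (0.95 × 0.60 + 0.05)/(0.95 × 0.30 + 0.05) = 0.62/0.335 = 1.85. The first row shows the effect of the fix: with no entry by analysis-year admission, the observed ratio equals the true one.

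**The case against.** The strongest reply has four parts.

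- **There is a second route.** A CF complication qualifies without any admission, and the US list ends in a catch-all with a specify field. This stands. A reader might infer that patients with stable, never-admitted cardiac disease fall into the no-cardiac stratum; the protocol does not support that, since they can be recorded as a complication.
- **The admission route may be almost empty.** No cardiac reason is listed, so few may enter that way and the bias may be slight. This stands as to size: what the forms capture is in registry questionnaires that are not shown. It does not rescue the definition, which then points to a category missing from the protocol's own lists.
- **Look-back windows belong in the statistical analysis plan.** Partly fair. But using an admission as a route of entry is a protocol choice, stated three times. Section 9.3.2.3 defers the FEV₁ equations and the FVC and FEF analyses to that plan, not the cardiac definition.
- **The study is descriptive, with sparse data and limited power.** True, and acknowledged in sections 8.3, 9.3.4 and 9.9. That limits the weight of any single subgroup result, but section 9.9 does not mention this bias, and a larger sample would not remove it.

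Listing cardiac disease under outcomes in section 9.3.2.2 also means that on-treatment cases are not wholly lost. They are counted, but they cannot be separated from pre-existing disease.

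**Conclusion.** The point holds for the yes/no hospitalisation and serious-outcome comparisons in the US cardiac subgroup. As written, membership can follow from the outcome. The bias is towards no difference if entry by admission is equal in the two cohorts; otherwise its direction is unknown. Its size is also unknown, and the figures above show direction under assumed inputs, not an estimate.

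A reader might infer that the comparison is forced to no difference, or that every safety result in the subgroup is affected in the same way. Neither follows. Equality is forced only if every subgroup member enters by an analysis-year admission. Section 9.3.4.1 also plans more than a yes/no summary: "Frequency of hospitalisations will be calculated and will include the number of days of hospitalisation, and age at hospitalisation". Counts and days may be distorted but are not fixed at equality, and entry guarantees neither death nor transplantation taken alone.

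For hepatic impairment the shared fault is the missing date. Overlap with the serious composite is not shown, because section 9.3.2.2 does not say which complications are selected for it.

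**What to change.** - **Timing.** In section 9.3.2.3 and Table 4, define the cardiac and hepatic subgroups only from registry entries dated before ivacaftor start; for comparators, before the calendar date used for baseline FEV₁. Put the same timing rule in section 9.3.1.3 for the UK.
- **No double use.** State that an analysis-year admission is not a route into the subgroup. This also covers a patient who starts ivacaftor partway through the year after an admission earlier in that year.
- **Later entries.** Count cardiac or cirrhosis-complication entries first recorded after the start date as outcomes.
- **Reconciliation.** Align the US cardiac definition with the lists in section 9.3.2.2, saying which fields can hold a cardiac entry.

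The cost is wording plus use of earlier registry data. Section 9.4 says that the episode form captures hospitalisation dates and reasons and that the encounter form captures complications. The drawback is a smaller subgroup. In addition, the US start date is a derived encounter date (section 9.3.2.1), so timing is only as exact as that.

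Moving the comparison to the UK registry is not a remedy. UK hospitalisation covers only pulmonary-exacerbation admissions (section 9.3.1.2, Table 4), so other admissions could not be compared. It would also set aside the registry holding 1035 of the two registries' 1035 + 432 = 1467 G551D patients (71%; section 9.5), a share that says nothing about cardiac prevalence.
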